## **Protocol Title: Trial to Improve Multisensory Neural Processing, Language & Motor Outcomes in Preterm Infants**

---

study therapists and an independent observer in the laboratory study the videos prior to beginning implementation. During a common training phase, the observer scores the therapists on all aspects of the treatment, as indicated by the aforementioned script sequence. The therapists also score themselves on the fidelity rating scale in order to immediately compare their self-assessments with those of the observer. The training phase is concluded when there is 90% adherence to the protocol and concordance between therapists and observer scoring. This allows for development of a gold-standard non-therapist observer and back-up observers that will be used to monitor possible drift during the treatment phases.

A random sample of 10% of all MS treatment sessions will be video recorded and assessed for fidelity with the fidelity rating scale by the trained observer.

Twenty percent of the sessions coded for MS treatment fidelity will be randomly selected and independently recoded for fidelity by a second observer to estimate inter-observer reliability of the fidelity scores.

### **Assessment Methods**

Our outcomes (or constructs) of interest are listed in Table 1. These constructs are quantifiable using well validated tests and measures. Our primary outcome is multisensory response and our secondary outcome is neurodevelopmental outcomes, including sensory adaptation, motor, language, tactile processing, and speech sound differentiation.

**Protocol Title: Trial to Improve Multisensory Neural Processing, Language & Motor Outcomes in Preterm Infants**

Table 1

| Construct  | Procedure(s)                            | Timing                                     | Variable derived  | Variable type |
|--|---|--|---|---------------|
| Multisensory response (Auditory-Tactile processing) | ERP to simultaneous puff + speech sound | Pre and post intervention (near discharge) | Pre-Post change in amplitude at frontal scalp locations in 176-377 ms time window                           | continuous    |
|  |   |  | IMP: Percentage of time spent in near-typical neural activation   | continuous    |
| Sensory reactivity and adaptation to environment    | ITSP                                    | 9-12 months                                | Behavioral neurological threshold score (typical or atypical)   | nominal       |
|  |   |  | Raw score in sensory processing domain  | continuous    |
| Language  | Bayley III                              | 22-26 months                               | Composite standard score
Scaled standard scores for expressive and receptive components                  | continuous    |
| Motor   | Bayley III                              | 22-26 months                               | Composite standard score
Scaled standard scores for fine and gross components                            | continuous    |
|  | Neurological Exam                       | 9-12 months
22-26 months                |   |               |
| Tactile processing                                  | ERP to calibrated air puff              | Baseline/
After intervention            | Amplitude of response in 171-240 time window at central and frontal scalp locations                         | continuous    |
| Functional tactile connectivity                     | ERP to calibrated air puff              | Baseline/
After intervention            | Absolute clustering coefficient of alpha band coherence network   | continuous    |
| Speech Sound differentiation                        | ERP to 6 speech sounds                  | Baseline/
After intervention            | Difference in absolute amplitude between /du/ and /gu/ in frontal scalp locations in 250-350 ms time window | continuous    |

**Primary Outcome Measures**

Sensory processing measurement by ERP:

*ERP Recording:* A high-density array of 128 electrodes embedded in soft sponges (Hydrocel Sensor Net, EGI, Inc., Eugene, OR) will be used to record ERPs with a sampling rate of 1000 Hz, filters set to 0.1-400 Hz (Figure 2a). Recording of brainwaves will be controlled by Net Station (v. 4.3; EGI, Inc., Eugene, OR). E-Prime (v. 4.0, PST, Inc., Pittsburgh, PA) software will control stimulus delivery.

*Stimulus-presentation paradigm:* The ERP procedure involves blocks of trials from four conditions: multisensory (simultaneous speech sound-puff), puff alone, speech sound alone, and sham puff in a randomly generated sequence. To prevent habituation, no more than 2 repetitions of a condition occur in a row, with inter-trial intervals varying randomly between 2000-2500 ms.

The “light touch” stimulus is an air puff emanating from a nozzle positioned above the skin of the palmar surface of the right hand secured in a mold holder (Figure 2b). Another mold holder connected to the second nozzle is placed 15 cm away at midline (sham condition). The pressure

## Protocol Title: Trial to Improve Multisensory Neural Processing, Language & Motor Outcomes in Preterm Infants

at the skin surface is 5 psi, or less than the pressure of the smallest microfilament used to test for neuropathies. The entire test session generates 60 trials per condition and lasts 8-10 minutes. The speech sound condition is a computer-generated woman's voicing of one of six syllables (i.e. /ba/, /da/, /ga/, /bu/, /du/, /gu/) delivered in a free field setting using a microphone placed at midline 15 cm. The speech stimuli are computer-synthesized consonant-vowel syllables from the "transition-only" stimulus series. The five-formant syllables were synthesized on a Klatt (cascade) synthesizer, so that the amplitude of individual formants was modulated as a function of the respective formant frequencies. The central frequencies of the steady-state portion of the formants were kept constant across the different consonants and only varied as a function of the vowel sounds. The syllables are presented at 65 dB SPL(A). More than the 2 key stimuli (/bu/ and /gu/) are presented to prevent habituation. The stimulus presentation paradigm simultaneous allows collection of multi- and uni-sensory conditions and the replication of prior-identified time windows and scalp regions that quantify individual differences in multi- or uni-sensory processing.

*Preparation and analysis of ERP data:* The recorded data will be filtered using a 0.3-40 Hz bandpass filter and segmented on stimulus onset to include a 200-ms prestimulus baseline and a 500-ms post-stimulus interval. Electrodes will be referred to Cz and re-referenced offline to an average reference. Resulting segments will be screened for motor/ocular artifacts using standard algorithms in NetStation, followed by a manual review.

We will utilize the time windows and electrode clusters identified in our previously published and preliminary data (Section C1) to guide computation of the mean amplitude for each patient, condition and time point using NetStation statistical extraction tools.

*Index of multisensory processing (IMP):* We have already identified template maps over the cumulative 500ms post-stimulus time window using a topographic cluster analysis (i.e., Topographic Atomize & Agglomerate Hierarchical Clustering approach) (see Preliminary Data section) for full-term (FT) and preterm (PT) infants, which accounted for 96.3% of the global explained variance in ERP response to the MS stimulus. Different pairs of template maps have been identified for the 3 time windows corresponding to previously-identified microstates during the multi-sensory condition (127-175ms, 176-377ms, 378-599ms). Using a within-participant spatial correlation process (i.e., cases are electrodes and the two variables are (a) participant's ERP and (b) template map value), we can identify which template map (FT or PT) best fits each time sample's observed topographical data for each participant.

This fitting procedure will be carried out for each of the 3 time windows. From this procedure, we calculate the percentage of time the topographical pattern of the participant's ERP to MS stimuli is most like the FT template map. We call this index the IMP. This index is expressed as a percentage from 100% (all time samples show nearly-typical activation) to 0% (no time samples show nearly-typical activation).

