**Table 1**

| Construct   | Procedure(s)                     | Timing                              | Variable derived   | Variable type |
|--|---|--|---|----------------------|
| Multisensory response (Auditory-Tactile processing) | ERP to simultaneous puff + speech sound | Pre and post intervention (near discharge) | Pre-Post change in amplitude at frontal scalp locations in 176-377 ms time window                           | continuous           |
|  |   |  | IMP: Percentage of time spent in near-typical neural activation   | continuous           |
| Sensory reactivity and adaptation to environment    | ITSP                                    | 9-12 months                                | Behavioral neurological threshold score (typical or atypical)   | nominal              |
|  |   |  | Raw score in sensory processing domain  | continuous           |
| Language  | Bayley III                              | 22-26 months                               | Composite standard score
Scaled standard scores for expressive and receptive components                  | continuous           |
| Motor   | Bayley III                              | 22-26 months                               | Composite standard score
Scaled standard scores for fine and gross components                            | continuous           |
|  | Neurological Exam                       | 9-12 months
22-26 months                |   |                      |
| Tactile processing                                  | ERP to calibrated air puff              | Baseline/
After intervention            | Amplitude of response in 171-240 time window at central and frontal scalp locations                         | continuous           |
| Functional tactile connectivity                     | ERP to calibrated air puff              | Baseline/
After intervention            | Absolute clustering coefficient of alpha band coherence network   | continuous           |
| Speech Sound differentiation                        | ERP to 6 speech sounds                  | Baseline/
After intervention            | Difference in absolute amplitude between /du/ and /gu/ in frontal scalp locations in 250-350 ms time window | continuous           |

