### **Analysis Plan**

#### **Power/Sample Size**

A total sample size of 230 (115 in each group) will be recruited. Although attrition in past similar work has been much lower, we estimate power under an assumption of 10% attrition (i.e., 180). Because pilot studies afford effect size estimates with wide confidence intervals due to small sample sizes, power analysis results were conducted for the effect size available from pilot data and lowest effect size that the after-attrition sample size affords. Feasibility of the expected effect size is then evaluated. Power analyses are based on primary variables (multi- and uni- sensory processing). If between-group differences occur on the putative covariates (i.e., pretreatment variables related to the outcomes) and they are associated with putative mediators or outcomes, the pretreatment variables will be statistically controlled after ensuring that the homogeneity of slopes assumption has been met. Pretreatment ERP variables will be statistically controlled regardless of the effect size of between-group differences to improve effect size estimates. Missing data will be handled using multiple imputation.

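### The primary outcome has two unranked variables, frontal amplitude change and the IMP, with no alpha, order or multiplicity rule, and the power section also calls unisensory measures primary

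*Combined protocol and SAP*

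**What the plan says.** All references are to the combined protocol and SAP.

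- **Assessment Methods** ranks the outcomes: "Our primary outcome is multisensory response and our secondary outcome is neurodevelopmental outcomes, including sensory adaptation, motor, language, tactile processing, and speech sound differentiation". The primary outcome is therefore a construct, and two unisensory measures are secondary.
- **Table 1** lists two continuous variables for that construct. One is "Pre-Post change in amplitude at frontal scalp locations in 176-377 ms time window". The other is "IMP: Percentage of time spent in near-typical neural activation", with no time window. Neither is put first.
- **Primary Outcome Measures, paragraph on the IMP**: "Different pairs of template maps have been identified for the 3 time windows" (127-175, 176-377 and 378-599 ms), and "This fitting procedure will be carried out for each of the 3 time windows". The result is then named in the singular: "We call this index the IMP". No sentence pools the windows or selects one.
- **Preparation and analysis of ERP data** cuts segments that end 500 ms after the stimulus.
- **Statistical Analysis, Aim 1** tests the group difference on multisensory processing measured by ERP and names no variable. The Aim 2 mediator is left equally open. Power for Aim 1 is for a single 1-tailed test.
- **Power/Sample Size** states: "Power analyses are based on primary variables (multi- and uni- sensory processing". This conflicts with Assessment Methods.

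No section gives a significance level, a hierarchy, an adjustment, or a rule on whether one or both variables must succeed.

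**The concern.** With two variables behind one primary claim and no rule linking them, a significant result on either could be reported as success. The false-positive rate for the headline claim would then exceed the level used for each test. The variable that carries the claim, and the definition of the IMP, could also be settled after the results are known. The same gap reaches Aim 2, whose first path is the treatment effect on the unnamed multisensory measure. The conflict over the unisensory measures adds doubt about which variables are primary at all.

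**Working it through.** **Inputs.** Two primary variables (Table 1), or four if the IMP is analysed once per window (1 amplitude + 3 IMPs). 1-tailed test, 180 analysed, g = 0.74 and 0.35 (Statistical Analysis). The documents give neither an alpha nor a correlation between the measures, so I assume 0.05 per test, one-sided as in the power text, and a correlation between test statistics from 0 to 0.9.

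**The plan's own power figure.** Power = Φ(g·√(n/2) − 1.645), with n = 90 per arm and √45 = 6.708.

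- g = 0.74: 4.964 − 1.645 = 3.319, so 99.95%. The stated figure of over 99% is reproduced.
- g = 0.35: 2.348 − 1.645 = 0.703, so 75.9%. The stated figure of over 80% is not reproduced. The 180 is 0.9 × 200, the superseded sample size; 0.9 × 230 = 207, which gives 80.9%. This is a separate matter, and the present point does not depend on it.

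Both figures are for one test.

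**Familywise error.** For k independent tests it is 1 − 0.95^k: 1 − 0.9025 = 9.75% for k = 2, and 1 − 0.8145 = 18.5% for k = 4. For correlated tests I used simulated equicorrelated normal statistics (400,000 draws), counting only results in the claimed direction:

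| Correlation | 0 (exact) | 0.3 | 0.5 | 0.7 | 0.9 |
|---|---|---|---|---|---|
| Two tests | 9.75% | 9.3% | 8.9% | 8.0% | 6.8% |
| Four tests | 18.5% | 16.4% | 14.5% | 12.0% | 8.8% |

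Every entry is above 5%.

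**What control would cost.** Power at g = 0.35, one-sided, normal approximation:

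| Approach | Alpha on first or each test | 180 analysed | 207 analysed |
|---|---|---|---|
| Fixed sequence, first test | 0.05 | 75.9% | 80.9% |
| Bonferroni, two tests | 0.025 | 65.1% | 71.2% |
| Bonferroni, four tests | 0.0125 | 54.2% | 60.9% |

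At g = 0.74 power stays above 99% in every row. Moving the first test to two-sided 0.05 would also give 65.1% with 180 analysed, because it too leaves 0.025 in the claimed direction.

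**The third IMP window.** It runs from 378 to 599 ms, a span of 221 ms, but the segment ends at 500 ms. So 599 − 500 = 99 ms, or 99/221 = 45% of the window, lies outside the data as segmented. Neither a separate IMP for that window nor an index pooled over all three can be computed in full as written.

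**The case against.** The strongest reply is that the problem is smaller than it may look.

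- **Four tests.** A reader might infer four primary tests and an error near 19%. The documents do not establish that. The IMP is named in the singular, its scale runs to 100% when all time samples look near-typical, and Table 1 has one IMP row. One index built from window-specific templates is the more natural reading, so two is the better-supported count. The objection stands to that extent; four remains an upper reading because no pooling rule is written.
- **Unisensory measures.** A reader might add speech and touch and infer six primary tests. The Aim 1 ERP test covers multisensory processing only. Speech and touch enter the analysis plan as mediators under the exploratory Aim 3, and a result on either could not show more typical multisensory processing. Their label in the power section is a wording conflict to correct and adds nothing to the familywise error.
- **Alpha and success rule.** A reader might infer that the plan tests each variable at 0.05 and accepts any one success. It says neither. If both variables had to succeed, there would be no inflation. But the plan does not say that either, and its silence is the defect.
- **Correlation.** Both variables come from the same recordings and may be strongly correlated. At 0.9 the two-test error falls to 6.8%, which is modest but still above 5%.
- **Window overrun.** The mismatch concerns how the IMP is measured and is not evidence about error control. That is right. It belongs here because the IMP cannot be ranked until it is defined.

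**Conclusion.** The concern holds for two unranked primary variables without an alpha, an order or a multiplicity rule. The familywise error is about 7-10% for two tests (correlation 0.9 down to 0), and about 9-19% if the IMP is tested in each window. These figures rest on one-sided 0.05 per test, on either result being able to carry the claim, and on a correlation that the documents do not report; they are a range and not an estimate. The conflict between Power/Sample Size and Assessment Methods over the unisensory measures is certain on the text. This should be corrected before unblinding. It does not by itself undermine the design.

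**What to change.** Before unblinding, amend the analysis plan as follows.

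1. State the alpha and name one primary variable. Test the other in fixed sequence, only if the first succeeds. Keep the 1-tailed basis of the power calculation; a move to two-sided testing is a separate decision with its own power cost (75.9% to 65.1% at g = 0.35 with 180 analysed).
2. Choose the order on scientific grounds. The 176-377 ms amplitude already has one window and one region. The IMP is closer to the stated aim, because it measures resemblance to the full-term pattern. Either can go first.
3. Define the IMP as one index, either pooled by a stated rule or taken from one named window. Any other window-specific IMP is secondary.
4. Reconcile the 378-599 ms window with the 500-ms post-stimulus segment.
5. Correct Power/Sample Size so that the unisensory measures are secondary, as in Assessment Methods.
6. Name the multisensory variable that serves as the Aim 2 mediator.

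The cost is wording only: no added infants and no alpha lost on the first test at the plan's sidedness. The downside is that the second variable is confirmatory only if the first succeeds. If the team wants either variable to be able to carry the claim alone, a Bonferroni split would do it, at the power shown in the working.

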## **Secondary Outcome Measures**

### *Baby Care Questionnaire (BCQ):*

The BCQ is a parent questionnaire that assesses the degree of parental structure and parental attunement. The three sections include sleeping, feeding, and soothing. Parents are asked to indicate their feelings about each statement by circling strongly agree (SA), agree (A), disagree (D), or strongly disagree (SD). The tool is validated for parents expecting a baby through 24 months of age.

### *Hammersmith Neonatal/Infant Neurological Examination (HNNE/HINE):*

The HNNE and HINE is a neonatal/infant neurological examination consisting of 34 items to assess tone, tone patterns, reflexes, movements, abnormal signs, and behavior.

### *Parenting Styles and Dimensions Questionnaire (PSDQ):*

The PSDQ is a 32-item parent questionnaire that assesses parenting style based on a series of items scored by parents along a 5-point Likert-type scale.

### *Infant Toddler Sensory Profile (ITSP):*

The ITSP is the most validated test for the behavioral evaluation of sensory processing. This parent-rated questionnaire has 48 questions, addressing five sensory processing sections (Auditory, Visual, Tactile, Vestibular, and Oral Sensory Processing) and a General measure. One variable from this instrument is the infant's neurological threshold (tendency to respond to sensory stimuli). 'Low neurological threshold' reflects situations when minimal sensory input causes a system to respond and 'high neurological threshold' reflects situations when a large amounts of stimulation is required before a response is registered. Typical, atypical high and atypical low ranges are provided for neurological threshold scores in the 7-12 month age band using published norms on 589 term-born American infants generating nominal variables.

Raw individual section scores are also provided. The ITSP has been used in large studies of preterm infants.

### *Bayley Scales of Infant and Toddler Development (Bayley III) — 3rd Edition:*

The Bayley III is the gold standard for the evaluation of former NICU graduates, especially preterm infants. We will use the language and motor composite standard scores for CA. The Bayley is currently administered in the Follow-Up Clinic by trained examiners who undergo yearly retraining by a Gold-standard examiner.

### *Preschool Language Scales (PLS5) - 5th Edition*

## **Protocol Title: Trial to Improve Multisensory Neural Processing, Language & Motor Outcomes in Preterm Infants**

---

The PLS-5 is a language assessment tool administered by a trained professional in which children point or verbally respond to pictures or objects. It assesses both receptive and expressive language skills in young children.

### *Child Behavior Checklist (CBCL)*

The CBCL is a 113-question standardized checklist used to detect social-emotional and behavioral concerns in young children. The form is filled out by parents and uses a 3-point Likert-type scale.

### **Analysis Plan**

#### **Power/Sample Size**

A total sample size of 230 (115 in each group) will be recruited. Although attrition in past similar work has been much lower, we estimate power under an assumption of 10% attrition (i.e., 180). Because pilot studies afford effect size estimates with wide confidence intervals due to small sample sizes, power analysis results were conducted for the effect size available from pilot data and lowest effect size that the after-attrition sample size affords. Feasibility of the expected effect size is then evaluated. Power analyses are based on primary variables (multi- and uni- sensory processing). If between-group differences occur on the putative covariates (i.e., pretreatment variables related to the outcomes) and they are associated with putative mediators or outcomes, the pretreatment variables will be statistically controlled after ensuring that the homogeneity of slopes assumption has been met. Pretreatment ERP variables will be statistically controlled regardless of the effect size of between-group differences to improve effect size estimates. Missing data will be handled using multiple imputation.

